Amiodarone Anastrozole Aprenavir Azithromycin Bromocriptine Cannabinoids Cimetidine Cisapride Clarithromycin Clotrimazole Cyclosporine Danazol Delavirdine Dexamethasone Diethyldithiocarbamate Diltiazem Dirithromycin Disulfiram Entacapone (high dose) Erythromycin Ethinyl estradiol Fluconazole Fluoxetine Fluvoxamine Gestodene Grapefruit juice Indinavir Isoniazid Itraconazole	Ketoconazole Metronidazole Mibepradil Miconazole Nefazodone Nelfinavir Nevirapine Norfloxacin Norfluoxetine Omeprazole Oxiconazole Paroxetine Propoxyphene Quinidine Quinine Quinupristin and dalfopristin Ranitidine Ritonavir Saquinavir Sertindole Sertraline Telithromycin Troglitazone Troleandomycin Valproic acid Verapamil Zafirlukast Zileuton

Appendix 2
List of Drugs with Potential Interactions
Examples of medications known to prolong the QT interval and/or induce Torsades De Pointes (TDP)

It has been recognized for a number of years that certain prescription medications can prolong the QT/QTc interval and cause a form of acquired Long QT syndrome, known as drug induced LQTS. The drugs that prolong the QT interval and/or have a risk of inducing Torsades de Pointes (TdP) are listed below. We have divided these into two groups based on their known or perceived risk of causing TdP:

A. Group 1: Drugs that are generally accepted by authorities to have a risk of causing Torsades de Pointes

Concomitant use of these drugs is not allowed during the study or within 2 weeks of randomization (at least four weeks for levomethadyl). These drugs should also be avoided for **up to 4 weeks following discontinuation of study treatment:**

Table 1 Group 1 Drugs^a

Generic Name	Class/Clinical Use	Comments
Amiodarone	Anti-arrhythmic/abnormal heart rhythm	Females>Males, TdP risk regarded as low
Arsenic trioxide	Anti-cancer/Leukemia	
Astemizole	Antihistamine/Allergic rhinitis	No Longer available in U.S.
Azithromycin	Antibiotic/bacterial infection	
Bepridil	Anti-anginal/heart pain	Females>Males
Chloroquine	Anti-malarial/malaria infection	
Chlorpromazine	Anti-psychotic/Anti-emetic/schizophrenia/nausea	
Cisapride	GI stimulant/heartburn	No longer available in U.S.
Citalopram	Anti-depressant/depression	
Clarithromycin	Antibiotic/bacterial infection	
Disopyramide	Anti-arrhythmic/abnormal heart rhythm	Females>Males
Dofetilide	Anti-arrhythmic/abnormal heart rhythm	Females > Males
Domperidone	Anti-nausea/nausea	Not available in U.S.
Droperidol	Sedative;Anti-nausea/anesthesia adjunct, nausea	
Erythromycin	Antibiotic;GI stimulant/bacterial infection; increase GI motility	Females>Males
Flecainide	Anti-arrhythmic/abnormal heart rhythm	
Halofantrine	Anti-malarial/malaria infection	Females>Males
Haloperidol	Anti-psychotic/schizophrenia, agitation	TdP risk with I.V. or excess dosage
Ibutilide	Anti-arrhythmic/abnormal heart rhythm	Females>Males

Table 1**Group 1 Drugs^a**

Generic Name	Class/Clinical Use	Comments
Levomethadyl	Opiate agonist/pain control, narcotic dependence	Not available in U.S.
Mesoridazine	Anti-psychotic/schizophrenia	
Methadone	Opiate agonist/pain control, narcotic dependence	Females>Males
Moxifloxacin	Antibiotic/bacterial infection	
Pentamidine	Anti-infective/pneumocystis pneumonia	Females>Males
Pimozide	Anti-psychotic/Tourette's tics	Females>Males
Probucol	Antilipemic/Hypercholesterolemia	No longer available in U.S.
Procainamide	Anti-arrhythmic/abnormal heart rhythm	
Quinidine	Anti-arrhythmic/abnormal heart rhythm	Females>Males
Sotalol	Anti-arrhythmic/abnormal heart rhythm	Females>Males
Sparfloxacin	Antibiotic/bacterial infection	No longer available in U.S.
Terfenadine	Antihistamine/Allergic rhinitis	No longer available in U.S.
Thioridazine	Anti-psychotic/schizophrenia	
Vandetanib	Anti-cancer/Thyroid cancer	
(*Does not apply to this study)		

^a Source: www.QTdrugs.org. Last revised: 17 May 2012

B. Group 2: Drugs that in some reports may be associated with Torsades de Pointes but at this time lack substantial evidence of causing Torsades de Pointes.

Concomitant use of these drugs is not allowed within 2 weeks of randomization or during the study. These drugs will be allowed during the study, at the discretion of the Investigator, if considered absolutely necessary. In such cases, the patient must be closely monitored, including regular checks of QTc and electrolytes (reference Section 5.6.2 of the protocol).

Table 2**Group 2 Drugs^a**

Generic Name	Class/Clinical Use	Comments
Alfuzosin	Alpha1-blocker/Benign prostatic hyperplasia	
Amantadine	Dopaminergic/Anti-viral/Anti-infective/ Parkinson's Disease	
Artemether + piperaquine	Anti-malarial/	Not available in U.S.
Atazanavir	Protease inhibitor/HIV	
Chloral hydrate	Sedative/sedation/ insomnia	
Clozapine	Anti-psychotic/schizophrenia	
Dolasetron	Anti-nausea/nausea, vomiting	

Table 2**Group 2 Drugs^a**

[figure not shown]
Generic Name	Class/Clinical Use	Comments
Dronedarone	Anti-arrhythmic/Atrial Fibrillation	
Eribulin	Anti-cancer/metastatic breast neoplasias	
Escitalopram	Anti-depressant/Major depression/Anxiety disorders	
Famotidine	H2-receptor antagonist/Peptic ulcer/ GERD	
Felbamate	Anti-convulsant/seizure	
Fingolimod	Immunosuppressant/Multiple Sclerosis	
Foscarnet	Anti-viral/HIV infection	
Fosphenytoin	Anti-convulsant/seizure	
Gatifloxacin	Antibiotic/bacterial infection	Oral/I.V. forms no longer available in U.S. and Canada, only ophthalmic
Gemifloxacin	Antibiotic/bacterial infection	
Granisetron	Anti-nausea/nausea and vomiting	
Iloperidone	Antipsychotic, atypical/Schizophrenia	
Indapamide	Diuretic/stimulate urine & salt loss	
Isradipine	Anti-hypertensive/high blood pressure	
Lapatinib	Anti-cancer/breast cancer, metastatic	
Levofloxacin	Antibiotic/bacterial infection	
Lithium	Anti-mania/bipolar disorder	
Moexipril/HCTZ	Anti-hypertensive/high blood pressure	
Nicardipine	Anti-hypertensive/high blood pressure	
Nilotinib	Anti-cancer/Leukemia	
Octreotide	Endocrine/acromegaly, carcinoid diarrhea	
Ofloxacin	Antibiotic/bacterial infection	
Ondansetron	Anti-emetic/nausea and vomiting	
Oxytocin	Oxytocic/Labor stimulation	
Paliperidone	Antipsychotic, atypical/Schizophrenia	
Perflutren lipid microspheres	Imaging contrast agent/Echocardiography	
Quetiapine	Anti-psychotic/schizophrenia	
Ranolazine	Anti-anginal/chronic angina	
Risperidone	Anti-psychotic/schizophrenia	
Roxithromycin*	Antibiotic/bacterial infection	*Not available in U.S.
Sertindole	Antipsychotic, atypical/Anxiety, Schizophrenia	Not available in U.S.

Table 2**Group 2 Drugs^a**

Generic Name	Class/Clinical Use	Comments
Sunitinib	Anti-cancer/RCC, GIST	
Tacrolimus	Immunosuppressant/Immune suppression	
Tamoxifen	Anti-cancer/breast cancer	
Telithromycin	Antibiotic/bacterial infection	
Tizanidine	Muscle relaxant/	
Vardenafil	phosphodiesterase inhibitor/vasodilator	
Venlafaxine	Anti-depressant/depression	
Voriconazole	Anti-fungal/anti-fungal	
Ziprasidone	Anti-psychotic/schizophrenia	

^a Source: www.QTdrugs.org. Last revised: 17 May 2012

Appendix 3: Preoperative toxicity visit flowchart

Appendix 4
Randomized, Controlled, Double-Blinded Trial Investigating the Effect of Vandetanib on Cellular Markers of Proliferation and Apoptosis in Breast Cancer

[name], PhD

INSTRUCTIONS FOR THE PATIENT: This is a monthly calendar on which you are to record which days you have taken your Vandetanib. Be sure you have enough calendars to last until your next appointment. If you develop any side effects from the pill, mark this on the calendar.
Bring the unused pills and your calendars with you at your next appointment
This diary is for your **Vandetanib** only

If you have any questions contact: _____

Telephone: _____

Your next appointment is: _____

VANDETANIB DIARY 300 mg daily

Week of	Sunday	Monday	Tuesday	Wednesday	Thursday	Friday	Saturday
Week of	Sunday	Monday	Tuesday	Wednesday	Thursday	Friday	Saturday
Week of	Sunday	Monday	Tuesday	Wednesday	Thursday	Friday	Saturday
Week of	Sunday	Monday	Tuesday	Wednesday	Thursday	Friday	Saturday
Week of	Sunday	Monday	Tuesday	Wednesday	Thursday	Friday	Saturday

Patient's signature: _____ date: _____

Appendix 5
Data and Safety Monitoring Plan

HCCC Clinical Trial Data and Safety Monitoring Plan (DSMP)

Date: 2/19/2013

IRB#: 201301763

Study Title: A Randomized, Double-Blind, Placebo-Controlled Trial Investigating the Effect of Vandetanib on Cellular Markers of Proliferation and Apoptosis in Invasive Breast Cancer

Principal Investigator: [name], PhD

Co-Investigators:

[name] Department of Surgery

[name] Department of Surgery

[name] Department of Internal Medicine

[name] Department of Pathology

[name] Biostatistician

All investigator-initiated protocols will be subject to ongoing monitoring of accrual, subject eligibility, protocol modifications and continuing reviews. Active studies will be audited for the DSMC by the CRSO, following guidelines based on level of risk to subjects. Audits will be conducted by reviewing subject files provided by clinical research coordinators, as well as original source documentation provided by online medical records and research pharmacists. The CRSO will review adverse events, eligibility of subjects, and adherence to the IRB- and PRMC-approved protocol. Protocols found to have discrepancies will be require a response from the PI and an action plan for correcting identified deficiencies. The DSMC will provide a schedule of audit and report dates if requested. **Type of Clinical Trial (check all that apply):**

Investigator-initiated (Iowa)

Investigator-initiated, multi-center (non-Iowa)

- Is this study monitored by an outside DSMB? Yes No

Compassionate-use drug protocol

Pilot study

Phase I

Phase I/II

Phase II

Phase III

Phase IV

Study risk-level (refer to attached risk-level assessment for this study):

Level 1—low risk of morbidity or death, * <<1% of death or any adverse event

Level 2—risk of death* <1% or any adverse event 1% – 5%

Level 3—risk of death* 1% – 5% or grade 4 – 5 SAE 1% – 5%

Level 4—risk of death* >5% or grade 4 – 5 SAE >15%

Drugs being used on a “compassionate” basis

** Risk of death” refers specifically to 100-day treatment-related mortality*

The following additional documents will be included in the DSMP for this study:

- A subject eligibility check-list (inclusion / exclusion criteria), which will be available in OnCore, the HCCC CTMS
- A list of expected toxicities and stopping rules for suspension of accrual secondary to adverse events and safety parameters
- A signed and dated statement from the Principal Investigator(s) declaring any conflict of interest (or lack thereof) with a description of how a conflict of interest will be monitored to enhance transparency
- The Human Subjects application will be obtained from HawkIRB
- Future Continuing Review and/or Modification forms will be obtained from HawkIRB
- For multi-centered trials, a detailed description of the procedures in place at each center that enable communication between participating centers such that the PI is aware of the status of participating subjects including the immediate (<24hours – week day) awareness of grade 4 – 5 SAE / death

Risk Level 3

- An independent Study Monitor, or the DSMC Chair (or his designee), will review study data (provided by the PI and CRSO) and communicate with the PI at least twice yearly. The proceedings of this meeting will be summarized by the CRSO in a brief letter to the PI, a copy of which will be forwarded to the DSMC.
- Principal Investigator will provide a QUARTERLY report to the Study Monitor and the CRSO for the DSMC, or data may be obtained from OnCore:
 - Quarterly patient accrual data
- Copies of all Serious Adverse Events will be reported to the CRSO as per DSMC reporting guidelines.
- CRSO will conduct a BIANNUAL audit of at least 25% of the subjects' research charts, and will report the results to the DSMC. Audits will:
 - Validate eligibility of patients accrued to the study
 - Check for the presence of a signed informed consent
 - Determine compliance with protocol methodology
 - Determine whether SAEs are being reported to internal and external regulatory agencies
 - Compare veracity of data in the research record with the primary source documents
 - Review investigational drug processing and documentation.

Assess cumulative AE/SAE reports for trends and compare to study stopping rules.

Routine Adverse Event Reporting

Routine reporting of adverse events to the DSMC via the CRSO is described in Table 1:

Table I: Routine Reporting of Adverse Events

Attribution	Adverse Event				
	Grade 1	Grade 2	Grade 3	Grade 4	Grade 5
Unrelated	Not required	Not required	CRSO	CRSO	CRSO
Unlikely	Not required	Not required	CRSO	CRSO	CRSO
Possible	CRSO	CRSO	CRSO	CRSO	CRSO
Probable	CRSO	CRSO	CRSO	CRSO	CRSO
Definite	CRSO	CRSO	CRSO	CRSO	CRSO

Eligibility Criteria:

- Patient with core biopsy, pathology demonstrating invasive breast cancer, with planned surgical excision
- Female gender. There is an incidence of male breast cancer, but it is unclear if the etiology is the same and inclusion of males could confound results.
- Age ≥ 18 . Breast cancer, while not restricted only to adult women, is rare in the younger population.
- ECOG performance status ≤ 2 .
- Life expectancy of greater than 6 months.
- Patient able to willingly provide informed consent to participate

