6.0 Treatment Plan

Subjects meeting the eligibility requirements in Section 4.1 and who have given signed informed consent will start the treatment dose of Vandetanib 300 mg or placebo orally, daily, starting such time as to allow 7 to 14 doses with the 7th or 14th dose given on the morning of the operation. Patients will return to clinic the day before the scheduled operation or the morning of surgery for repeat laboratory studies and EKG. Costs of the post-treatment labs and EKG will be covered by the PI. The results will be reviewed and safety to proceed documented prior to the operation. The study calendar (which will be provided at the pretreatment office visit to document administration of the study drug and any side effects associated with treatment) will be reviewed, pill counts performed, and an adverse events assessment performed at that time. Any concerns related to toxicities and safety to proceed to surgery will be addressed with the attending surgeon at that time. Common induction anesthetics (isoflurane, desflurane and sevoflurane) can cause QTc prolongation. Any QTc (>440 ms) on EKG should be discussed with the attending anesthesiologist prior to induction, and these induction agents should not be used if QTc > 480 ms. A flow chart of the preoperative screening procedure is shown in appendix 3. Subjects will be instructed to take their medication at the same time each day. In general subjects should take their dose every day even if it is not at the recommended time. Specific questions regarding timing and doses can be directed to [name] [contact], [name]). Patients will be removed from the study for failure to take at least 80% of the study doses. Patients will not be replaced if they are removed from the trial.

Women of Childbearing Potential (WOCBP) must use *highly effective* methods of birth control (one method or a combination of methods that results in a less than 1% failure rate per year) throughout therapy and must maintain full contraception for at least 95 days after the last dose of Vandetanib.

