11.2 Adverse Event (AE and Serious Adverse Event [SAE])

11.2.1 Definitions

An **adverse event** (AE) is defined in the *CTEP, NCI Guidelines* [2005] as “any unfavorable and unintended sign (including an abnormal laboratory finding), symptom or disease temporally associated with the use of a medical treatment or procedure (attribution of unrelated, unlikely, possible, probably or definite).”

A **serious adverse event** (experience) or reaction is any untoward medical occurrence that at any dose: results in death, is life-threatening, requires inpatient hospitalization or prolongation of existing hospitalization, results in persistent or significant disability / incapacity, or is a congenital anomaly / birth defect. Hospitalization for planned surgical treatment of breast cancer does not constitute an SAE.

The definition of serious adverse event (experience) also includes *important medical event*. Medical and scientific judgment should be exercised in deciding whether expedited reporting is appropriate in other situations, such as important medical events that may not be immediately life-threatening or result in death or hospitalization but may jeopardize the subject or may require intervention to prevent one of the other outcomes listed in the definition above. These should also usually be considered serious. Examples of such events are intensive treatment in an emergency room or at home for allergic bronchospasm; blood dyscrasias or convulsions that do not result in hospitalization; or development of drug dependency or drug abuse.

The definition of “**related**” is that there is a reasonable possibility that the drug caused the adverse experience.

Investigators are required by Federal regulations to report serious adverse events as defined in the tables below. If a subject has a reportable serious adverse event, the Study Chair and the Institutional Review Board follow guidelines of this table. This study will utilize the Common Toxicity Criteria version 4.0 to determine the severity of the reaction for adverse event reporting.

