11.2.2 Assessment of Risk Level

The Data Safety Monitoring Plan (DSMP) can be found in Appendix 5 of this protocol.

This investigation involves a risk-level 3 procedure, in a population that should not be at any increased risk for complications.

11.2.3 Assessing Toxicity:

Toxicity will be graded according to NCI’s Common Toxicity Criteria (CTCAE v4). The investigator will determine relationship of toxicity to the investigational drug as unrelated, unlikely related, possibly related, probably related, or definitely related using standard criteria for clinical trials. All grades of toxicity will be noted and reported as directed in Table I: Clinical Data Update System (CDUS) Guidelines for Routine Adverse Event Reporting.

Patients who experience a CTCAE (version 4) Grade 3 or 4 toxicity that is considered related to Vandetanib will have their study drug stopped. If a patient discontinues treatment, safety follow-up visits will be performed according to the schedule of assessments and procedures. In addition, a 30 day follow up visit will occur if AEs have not resolved by the time of the post op safety visit. SAEs and study drug-related AEs must be followed until resolution unless in the Investigator’s opinion, the event is unlikely to resolve due to the patient’s underlying condition.

Cardiac toxicity - QTc prolongation

Electrocardiograms will be evaluated by suitably qualified personnel for the presence of QTc prolongation or other abnormalities, in particular, any changes in the T-wave morphology that would suggest a higher likelihood for the development of any arrhythmia. Any clinically significant abnormal findings or QTc prolongations will be recorded as AEs.

In addition to scheduled ECG, additional ECGs should also be performed in the event of QTc prolongation, both during and post the prolongation period.

- During the QTc prolongation period: For a single QTc value of >500 ms, Vandetanib must be withheld and patients will be removed from the study. Electrocardiograms will be followed at least once per week (done at the same day each week) along with electrolytes, until QTc falls \leq 480 ms.

Gastrointestinal toxicity

Nausea, vomiting, or both may be controlled with anti-emetic therapy. The use of somatostatin or a somatostatin analogue is allowed to control diarrhea.

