4.1.2 Exclusion Criteria

- Prolonged QT interval (QTc > 480 milliseconds) on screening EKG or congenital long QT syndrome
- Any concomitant medications that are known to be associated with Torsades de Pointes or QT elongation (see appendix 2).
- Hypertension not controlled by medical therapy (systolic BP greater than 160 mmHg or diastolic blood pressure greater than 100 mmHg).
- Patients taking metformin or digoxin. History of arrhythmia (multifocal premature ventricular contractions, bigeminy, trigeminy, ventricular tachycardia), which is symptomatic or requires treatment (CTCAE Grade 3), symptomatic or uncontrolled atrial fibrillation despite treatment, or asymptomatic sustained ventricular tachycardia. Patients with atrial fibrillation controlled by medication are permitted.
- Significant cardiac event (e.g., myocardial infarction), superior vena cava syndrome, New York Heart Association (NYHA) classification of heart disease ≥ 2 within 12 weeks, or presence of cardiac disease that in the opinion of the Investigator increases the risk of ventricular arrhythmia.
- Serum calcium or magnesium outside the institutional range of normal.
- Serum Potassium < 4.0 mmol/L or above 5.0 mmol/L
- Creatinine clearance < 50 ml/min
- PT > 12 seconds or PTT > 31 seconds
- Platelet count $< 100,000$
- Serum bilirubin greater than 1.5 mg/dl
- Alanine aminotransferase (ALT) > 50 U/L, aspartate aminotransferase (AST) > 65 U/L, or alkaline phosphatase (ALP) > 250 U/L
- Any cytotoxic treatments, such as neoadjuvant chemotherapy, planned before subsequent surgical procedure.
- Previous exposure to Vandetanib
- Previous enrollment or randomization in this study.
- Involvement in the planning and /or conduct of the study (applies to both Astra Zeneca staff and staff at UIHC).
- Previous or current malignancies of other histologies within the last 5 years, with the exception of in situ carcinoma of the cervix, and adequately treated basal cell or squamous cell carcinoma of the skin.
- Patients who have received prior surgical site radiation.
- Patients on CYP3A4 inhibitors or inducers (see appendix 1).
- Inability to test core biopsy for study markers
- Pregnancy or lactation at the time of study entry. (**Note: Pregnancy testing must be performed within 2 weeks prior to randomization according to institutional standards for women of childbearing potential.**)

Toxicities

Very Common (experienced by more than 10% of patients taking Vandetanib)

Headache
Diarrhea

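### The diary invites a blinded patient to judge cause before noting a symptom, which does not match the protocol's timing-based adverse-event definition (minor wording point)

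*Combined protocol and SAP*

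**What the plan says.** **Appendix 4 (patient diary)** tells the patient: "If you develop any side effects from the pill, mark this on the calendar".

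**Section 6.0** says the study calendar is handed out "to document administration of the study drug and any side effects associated with treatment". At the return visit shortly before surgery the calendar is reviewed, with "pill counts performed, and an adverse events assessment performed at that time".

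**Section 11.2.1** defines an adverse event by timing: "any unfavorable and unintended sign (including an abnormal laboratory finding), symptom or disease temporally associated with the use of a medical treatment or procedure". Judging its cause, on a scale that includes unrelated, is a separate step.

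**Section 11.2.3** assigns that step: "The investigator will determine relationship of toxicity to the investigational drug as unrelated, unlikely related, possibly related, probably related, or definitely related". It also requires toxicity of every grade to be noted.

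**Section 5.0** gives Drug Toxicity Evaluation its own row, apart from Study Drug Calendar. It is marked at Day 7-14, at the post-treatment safety visit and at follow-up. **Section 9.3** confirms a last toxicity evaluation at the post-operative visit.

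**Section 7.1** provides identical packages of drug and placebo, with the key held by the pharmacy service until the trial ends.

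**The concern.** The protocol separates two steps: a symptom is recorded because of when it occurred, and the investigator then judges its cause. The diary merges them and gives the first judgement to the patient, who does not know whether she is taking vandetanib or placebo and is waiting for cancer surgery. Several effects listed in Section 11.2.4 as very common with vandetanib (headache, trouble sleeping, fatigue, decreased appetite) are complaints she could readily put down to worry or to the disease. If she does, the instruction gives her no reason to write them down.

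At stake is how completely symptoms are captured as they happen. Dosing lasts 7 to 14 days, or up to 28 if surgery is moved (Section 10.1). A symptom not noted on the day depends on recall at a later assessment. Symptoms with a high background rate are also those for which the placebo arm is most useful, so it helps to record them in the same way whatever the patient believes about their cause.

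**Working it through.** The plan states no figure on this point, so the check is a comparison of texts followed by a look at what a size estimate would need.

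1. **Who judges cause, and when.** Under 11.2.1 and 11.2.3 the event is recorded first, on timing, and the investigator judges cause second. Under Appendix 4 the patient judges cause first, because what she marks are effects of the pill. The Section 6.0 phrase could be read as cause or as timing; beside the diary sentence, the causal reading is the natural one. The mismatch is real.

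2. **Other routes to the investigator.** The adverse-event assessment before surgery is listed in addition to the calendar review. The schedule marks Drug Toxicity Evaluation at three points, and Section 9.3 confirms the last. No passage limits these assessments to what the diary shows. Equally, no passage says that they ask about all symptoms, and no section describes how the Day 7-14 evaluation is done. The repeat EKG, blood pressure and laboratory tests do not depend on the diary, but they do not detect headache, poor sleep or fatigue.

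3. **What reporting would lose.** Table I in Section 11.2.4 sends every grade 3 to 5 event to the CRSO whatever its attribution. It sends grade 1 and 2 events only if attribution is at least possible. For routine reporting, the exposed group is therefore mainly grade 1 and 2 symptoms that were unmarked and unrecalled, and that the investigator would have called at least possible.

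4. **What a size estimate needs.** Let π be the true frequency of a symptom in an arm, a the share that patients blame on the pill and mark, and r the share of the remainder recovered at staff assessments. Then

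   recorded frequency = π × [a + (1 − a) × r].

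   If r = 1, this equals π whatever a is, so the diary wording costs nothing. If π and r are the same in both arms but a differs, with values a_V on vandetanib and a_P on placebo, the false difference is

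   π × (1 − r) × (a_V − a_P).

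   Both the loss and any distortion therefore shrink as r rises. The documents give no value for a or r and no background symptom rate for placebo, so neither quantity can be computed.

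5. **Link to the planned analysis.** The objectives in Section 2.0 concern tissue markers. Section 12.0 specifies tests of marker changes and no between-arm test of adverse events. Ki-67 is read from tissue and does not depend on the diary's symptom entries.

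**The case against.** The strongest reply is that this is loose lay wording with little consequence. A patient may well take side effects to mean anything new since she started the pill. Staff assess adverse events independently of the calendar, the investigator must note all grades, and both arms receive the same instruction. Most of this stands, and it is why the point is minor. It does not remove the mismatch: the sentence can be read causally, and the documents do not say that the staff assessments ask about symptoms the patient has not marked.

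A reader might infer three stronger things, none of which the documents support.

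- *That patients are told to leave out everything else.* They are not. The instruction does not restrict entries to pill-related effects. The one place where the diary uses the word only concerns which product the diary covers.
- *That the diary is the sole record during dosing, or controls what the investigator sees.* Sections 5.0, 6.0 and 9.3 provide separate assessments, one of them marked in the Day 7-14 column.
- *That the safety comparison between arms is biased by a definite amount.* A visible effect such as rash could lead a patient to guess that she is on drug and to blame the pill for other symptoms. That is a plausible mechanism, but the documents do not report it. It could also colour answers at interview, so new diary wording would reduce it without removing it.

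**Conclusion.** The concern holds as a wording mismatch. The diary, and less clearly Section 6.0, invites the patient to judge cause before recording, whereas Sections 11.2.1 and 11.2.3 record on timing and leave cause to the investigator. The likely loss is mild, transient symptoms that are blamed on something else, not noted on the day and not recalled at a visit. Some differential recording between arms is possible. Neither effect can be quantified from the documents, and the Ki-67 endpoint is unaffected.

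This rests on two assumptions: that at least some patients read the sentence causally, and that staff assessments recover much, but not all, of what goes unmarked. If they recover everything, the wording has no effect on whether a symptom is eventually recorded. Priority: minor and optional.

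**What to change.** Replace the Appendix 4 sentence with: *Write down any new or worse symptom and the date, whatever you think caused it.* Align the Section 6.0 phrase, so that the calendar is described as recording doses taken and any new or worsening symptoms. It would also help to state in Section 6.0 that the assessment before surgery asks about all symptoms, not just those marked.

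The attribution scale, Table I routing and the investigator's role stay as they are. The cost is one sentence on a patient form and a small edit to Section 6.0, plus a few more low-grade entries for staff to grade and attribute.
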